9.4.1.1.1. Olaratumab/Placebo

9.4.1.1.1.1. Infusion-Related Reactions

As with other monoclonal antibodies, hypersensitivity reactions may occur during or following olaratumab administration.

Patients treated with olaratumab/placebo should be closely monitored for signs and symptoms indicative of an infusion reaction by the medical staff from the start of the infusion until at least 1 hour after the end of the infusion in an area where emergency medical resuscitation equipment and other agents (epinephrine, prednisolone equivalents, etc.) are available.

Olaratumab/placebo infusion reactions will be defined according to the NCI-CTCAE version 4.0 definition of IRRs.

Symptoms occurring during or following infusion of investigational therapy may also be defined according to AE categories such as allergic reaction, anaphylaxis, or cytokine release syndrome (NCI-CTCAE version 4.0 section “Immune system disorders”). In the setting of symptoms or signs occurring during or following infusion of investigational therapy, investigators are encouraged to use the AE terms that best describe the event, and mark “yes” or “no” for hypersensitivity/IRR event flag.

For patients who experience a Grade 1 or 2 IRR, the infusion should be stopped and the patient treated with the following (or equivalent) medications: a histamine H1 antagonist (eg, diphenhydramine) and glucocorticoid (eg, dexamethasone) intravenously, acetaminophen, and oxygen (as indicated), according to standard medical practices. After recovery, the infusion rate should be decreased 50% for the duration of the infusion. After a Grade 1 or 2 IRR, patients should be premedicated with the following (or equivalent) medications: a histamine H1 antagonist (eg, diphenhydramine) and glucocorticoid (eg, dexamethasone) intravenously, and acetaminophen, as appropriate, approximately 30-60 minutes prior to all subsequent olaratumab/placebo infusions.

A Grade 3 or 4 IRR will require immediate treatment, including the use of epinephrine, bronchodilators, and/or glucocorticoids for symptomatic bronchospasm, IV fluids and/or

pressors for hypotension, and immediate and permanent discontinuation of olaratumab/placebo with appropriate supportive care.

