10.3.1.3. Adverse Events of Special Interest (AESI)

Adverse events of special interest are events that have been identified as safety signals during preclinical or early clinical trials or based on class effects of similar drugs. These events will be monitored prospectively in the clinical developmental program. Each event is defined by a careful assessment and grouping of individual related MedDRA preferred terms.

AESI for olaratumab/placebo

Infusion-related reactions

AESIs for combination of olaratumab/placebo and doxorubicin

Infusion-related reactions

Cardiac arrhythmias and cardiac dysfunction

Refer to Section 9.4.1.1 for special treatment considerations for dose delay, modifications, and discontinuations from olaratumab/placebo and doxorubicin, including adverse events of concern or special interest.

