5.2.1.2. Safety Analysis Variables

Definitions of variables for safety analysis are listed by category and alphabetically within category.

Adverse event (AE)-related variables are listed below:

- **Adverse event (AE)** is defined as any untoward medical occurrence in a patient administered a pharmaceutical product, without regard to the possibility of a causal relationship.

AEs of special interest (AESIs)

AESI for olaratumab:

- Infusion-related reactions (IRRs)

AESI for doxorubicin:

- Cardiac arrhythmias
- Cardiac dysfunction

AESI for the combination of olaratumab and doxorubicin:

- IRRs
- Cardiac arrhythmias
- Cardiac dysfunction

Notes.

Categories of AESI may be modified as the understanding of the safety of the investigational drug increases. The final list of categories will be maintained at both compound and study level and reported in the CSR.

Consolidated AEs are composite AE terms consisting of synonymous PTs to allow meaningful interpretation of the AE data. Consolidated AE categories and PTs will be maintained at compound and/or study level and reported in the CSR.

Serious adverse event (SAE) is any AE that results in one of the following outcomes:

- death
- a life-threatening experience (that is, immediate risk of dying)
- persistent or significant disability/incapacity
- initial or prolonged in-patient hospitalization
- congenital anomaly/birth defect
- considered significant by the investigator for any other reason

Treatment-emergent adverse event (TEAE) is defined as an event that first occurred or worsened in severity after baseline and up to 30-day short-term follow-up visit.

Exposure-related variables are listed below:

- **Number of dose level reductions:** Sum of the number of dose level reductions as reported in the eCRF
- **Dose delays:** As reported in the eCRF
- **Dose withheld/skip (Not Administered):** As reported in the eCRF
- **Dose interruption(intravenous hold due to IRR):** As reported in the eCRF

Olaratumab or placebo treatment:

- Duration of treatment (weeks; 21 days added to duration of treatment because administration is every 3 weeks [on Days 1 and 8 of each 3-week cycle]) = $([\text{Date of last cycle Day 1} - \text{date of first dose}] + 21) \div 7$
- Cumulative dose, dose intensity, and relative dose intensity:
 - Cumulative dose (mg/kg) = Sum of (dose administered at each infusion [mg] \div Last available weight [kg])

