5.14.2. Adverse Events

An adverse event (AE) is defined as any untoward medical occurrence in a patient administered a pharmaceutical product, without regard to the possibility of a causal relationship.

Treatment-emergent adverse event (TEAEs) are events that first occurred or worsened in severity after baseline and up to 30-day short-term follow-up visit. The MedDRA PT derived from the verbatim term will be used and severity is measured using the grade defined by the National Cancer Institute - Common Terminology Criteria for Adverse Events (NCI-CTCAE).

Study drug-related AEs are AEs that were considered to be at least possibly related to study drug by an investigator. Missing relationship is considered related to all study drugs.

Serious adverse events (SAEs) are any AEs that result in one of the following outcomes:

- death
- initial or prolonged inpatient hospitalization
- a life-threatening experience (that is, immediate risk of dying)
- persistent or significant disability/incapacity
- congenital anomaly/birth defect
- considered important by the investigator for any other reason

AEs of special interest (AESIs)

AESIs are events which have been identified as safety signals during preclinical or early clinical trials or based on class effects of similar drugs. These events will be monitored prospectively in

the clinical developmental program. Each event is defined by a careful assessment and grouping of individual related MedDRA PTs. The list of PTs for AESIs is in [Appendix 2](#).

AESI for olaratumab

- IRRs

AESI for doxorubicin

- Cardiac arrhythmias
- Cardiac dysfunction

AESI for the combination of olaratumab and doxorubicin

- IRRs
- Cardiac arrhythmias
- Cardiac dysfunction

Consolidated AEs include Abdominal Pain, Anemia, Fatigue, Hyperbilirubinaemia, Hypertension, Hypoalbuminaemia, Hypokalaemia, Hypomagnesaemia, Hyponatraemia, Hypoproteinemia, Intestinal Obstruction, Leukocytosis, Leukopenia, Lymphopenia, Mucositis, Neuropathy, Neutropenia, Musculoskeletal pain, Rash, and Thrombocytopenia. Each consolidated AE contains PTs identified as clinically identical or synonymous. The list of PTs for consolidated AEs is in the [Appendix 3](#).

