5.14.2.2. Treatment-Emergent Adverse Events (TEAEs)

An overview of TEAEs will be provided to summarize the number and percentage of patients with any:

- TEAE
- treatment-emergent SAE

- CTCAE Grade ≥ 3 TEAE
- $>5\%$ by experimental arm
- TEAE leading to death (on treatment and within 30 days of last dose of study drug)
- TEAE leading to discontinuation of olaratumab, chemotherapy, or any study drug
- TEAE leading to dose modification of any study drug, olaratumab, or chemotherapy
- TEAE leading to hospitalizations
- TEAE leading to transfusions
- TEAE by cycle

The numbers and percentages will be calculated based on overall (regardless of causality), possibly related to olaratumab, chemotherapy, or any study drug for the overview of TEAEs.

In addition, the following TEAE summaries will be provided (regardless of causality, and study-drug related):

- summary of TEAEs by SOC and PT
- summary of TEAEs by high level group term (HLGT) and high level term HLT
- summary of TEAEs by worst CTCAE grade and PT
- summary of TEAEs by PT and decreasing frequency
- summary of TEAEs by AESI and consolidated category and PT

A patient listing of all AEs will be provided.

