	Conjunctival oedema
	Corneal oedema
	Cytokine release syndrome
	Distributive shock
	Drug hypersensitivity
	Epiglottic oedema
	Eye oedema
	Eye swelling
	Eyelid oedema
	Face oedema
	First use syndrome
	Gingival oedema
	Gingival swelling
	Gleich's syndrome
	Hypersensitivity
	Idiopathic urticaria
	Infusion related reaction
	Kounis syndrome
	Laryngeal oedema
	Laryngotracheal oedema
	Limbal swelling
	Lip oedema

AESI	Preferred Term
	Lip swelling
	Oculorespiratory syndrome
	Oedema mouth
	Oropharyngeal swelling
	Palatal oedema
	Periobital oedema
	Pharyngeal oedema
	Scleral oedema
	Shock
	Swelling face
	Swollen tongue
	Tongue oedema
	Tracheal oedema
	Type 1 hypersensitivity
	Urticaria
	Urticaria cholinergic
	Urticaria chronic
Urticaria papular	
Infusion-related Reactions (9 additional PTs)	Abdominal pain
	Abdominal pain upper
	Abdominal pain lower
	Back pain
	Chills
	Dyspnoea
	Flushing
	Hypotension

	Pyrexia
--	---------

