Appendix 3. List of Preferred Terms for Consolidated AEs

Consolidated AE	Preferred Term
ABDOMINAL PAIN	Abdominal pain
	Abdominal pain lower
	Abdominal pain upper
ANAEMIA	Anaemia
	Haemoglobin decreased
	Red blood cell count decrease
FATIGUE	Asthenia
	Fatigue
HYPERBILIRUBINAEMIA	Blood bilirubin increased
	Hyperbilirubinaemia
HYPERTENSION	Hypertension
	Blood pressure increased
HYPOALBUMINAEMIA	Blood albumin decreased
	Hypoalbuminaemia
HYPOKALAEMIA	Blood potassium decreased
	Hypokalaemia
HYPOMAGNESAEMIA	Blood magnesium decreased
	Hypomagnesaemia
	Magnesium deficiency
HYPONATRAEMIA	Blood sodium decreased
	Hyponatraemia
HYPOPROTEINEMIA	Hypoproteinemia
	Protein total decreased

Consolidated AE	Preferred Term
INTESTINAL OBSTRUCTION	Gastrointestinal obstruction
	Intestinal obstruction
	Small intestinal obstruction
LEUKOCYTOSIS	Leukocytosis
	White blood cell count increased
LEUKOPENIA	Leukopenia
	White blood cell count decreased
LYMPHOPENIA	Lymphocyte count decreased
	Lymphopenia
MUCOSITIS	Apthous stomatitis
	Mucosal inflammation
	Oropharyngeal pain
	Stomatitis
MUSCULOSKELETAL PAIN	Arthralgia
	Back Pain
	Bone Pain
	Flank Pain
	Groin Pain
	Muscle Spasms
	Musculoskeletal Chest Pain
	Musculoskeletal Pain
	Myalgia
	Neck Pain
	Pain In Extremity
NEUROPATHY	Hypoaesthesia
	Neuropathy peripheral

	Paraesthesia
	Peripheral sensory neuropathy
NEUTROPENIA	Neutropenia
	Neutrophil count decreased
RASH	Dermatitis
	Dermatitis acneiform
	Dermatitis allergic
	Dermatitis bullous
	Rash
	Rash follicular
	Rash generalised
Consolidated AE	Preferred Term
	Rash macular
	Rash papular
	Rash pruritic
	Rash pustular
THROMBOCYTOPENIA	Platelet count decreased
	Thrombocytopenia

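### SAP 5.14.2 and Appendix 2 define the infusion-related reaction AESI by preferred terms alone, including nine non-specific terms with no stated infusion-timing condition, so the descriptive group rate, applied literally, is overstated in both arms

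*SAP*

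**What the plan says.** SAP 5.14.2 says of AESIs: "Each event is defined by a careful assessment and grouping of individual related MedDRA PTs". It refers to Appendix 2 for the terms. Protocol 10.3.1.3 uses the same rule: "Each event is defined by a careful assessment and grouping of individual related MedDRA preferred terms". IRR is the only AESI that either document lists for olaratumab on its own.

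In Appendix 2, besides a block of hypersensitivity-type terms, the row "Infusion-related Reactions (9 additional PTs" lists abdominal pain, abdominal pain upper, abdominal pain lower, back pain, chills, dyspnoea, flushing, hypotension and pyrexia.

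SAP 5.2.1.2 defines a treatment-emergent event as one that "first occurred or worsened in severity after baseline and up to 30-day short-term follow-up visit". SAP 5.14.3 tabulates treatment-emergent AESIs by group and PT, for all causes and for drug-related events, and adds a listing of IRR events. SAP 5.14.2.2 also plans a "summary of TEAEs by AESI and consolidated category and PT".

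Protocol 9.4.1.1.1.1 describes the clinical event differently: "Olaratumab/placebo infusion reactions will be defined according to the NCI-CTCAE version 4.0 definition of IRRs". For symptoms that arise during an infusion or after it, investigators choose the best-fitting AE term and mark a yes/no hypersensitivity/IRR flag. The SAP does not mention this flag.

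**The concern.** An infusion reaction is identified by its timing relative to an infusion. Abdominal pain, back pain, fever and breathlessness are also ordinary events in patients with advanced sarcoma receiving doxorubicin. If such a term counts whenever it occurs between baseline and the 30-day visit, the group total becomes a count of IRRs plus general symptoms.

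At stake is the headline rate for the one AESI attributed to olaratumab alone. Events unrelated to the infusion raise the rate in both arms. If they are equally common in both arms, they also shrink the difference and the ratio between arms, so a real excess on olaratumab could look smaller than it is. The premedication and antibody explorations in SAP 5.9 and 5.15 are optional and not tied to Appendix 2. They would be affected only if they used this grouping.

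**Working it through.** **Is there a condition anywhere in the SAP?** Nine additional terms are announced and nine are listed. The SAP text on IRRs or AESIs is in 5.2.1.2, 5.9, 5.11.4, 5.14.2, 5.14.2.2, 5.14.3, 5.15, 5.17.2 and Appendix 2. None of it states an onset window, a link to an infusion date, or use of the flag.

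**What literal application implies.** All three terms of the ABDOMINAL PAIN category in "Appendix 3. List of Preferred Terms for Consolidated AEs" are among the nine. In each arm the IRR patient count could therefore not be lower than the abdominal pain patient count, even with no infusion reaction at all. Back pain, 1 of the 11 MUSCULOSKELETAL PAIN terms, is also among the nine. This shows what the rule counts, not how many such events will occur.

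**Share of time near an infusion.** There are two infusion days per 21-day cycle. The counting window is about cycles × 21 + 30 days: 72, 114 and 198 days for 2, 4 and 8 cycles.
- Infusion days only: 4/72 = 5.6%, 8/114 = 7.0%, 16/198 = 8.1%.
- Infusion day plus the next day: 8/72 = 11.1%, 16/114 = 14.0%, 32/198 = 16.2%.

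These are shares of time, not of events.

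**Illustration of dilution.** The documents give neither the true IRR rate nor the background rate, so all rates here are assumptions: true IRR 10% vs 5%, and background b of 10%, 30% or 50%, equal in both arms and independent of true reactions.
- All-PT rate = 1 − (1 − IRR)(1 − b), so the difference is 5.0 × (1 − b).
- Window rule at 4 cycles with a constant background hazard: residual background r = 1 − (1 − b)^0.140, and rate = 1 − (1 − IRR)(1 − r).
- Window rule with 10% of true reactions late: in-window IRR is 9% vs 4.5%, so the difference is 4.5 × (1 − r).

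| b | All-PT rates (%) | Difference | r | Window rates (%) | Difference | Difference, 10% late |
|---|---|---|---|---|---|---|
| 10% | 19.0 vs 14.5 | 4.5 | 1.5% | 11.3 vs 6.4 | 4.93 | 4.43 |
| 30% | 37.0 vs 33.5 | 3.5 | 4.9% | 14.4 vs 9.6 | 4.76 | 4.28 |
| 50% | 55.0 vs 52.5 | 2.5 | 9.3% | 18.3 vs 13.8 | 4.54 | 4.08 |

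From 2 to 8 cycles, the window differences with no late reactions run from 4.94 to 4.92, 4.81 to 4.72 and 4.63 to 4.47.

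**Where the window stops helping.** With 10% late, the two differences are equal when 4.5(1 − b)^0.140 = 5(1 − b). Then (1 − b)^0.860 = 0.9, so 1 − b = 0.885 and b is about 11.5%. Below that background the window gives no gain in the difference. It still brings the level of the rate closer to the truth. At b = 10%, the window rates are 1 − 0.91 × 0.985 = 10.3% and 1 − 0.955 × 0.985 = 5.9%, against 19.0% and 14.5% under the all-PT grouping.

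**The case against.** The strongest reply is that the SAP is silent; it does not say that timing is irrelevant. It speaks of careful assessment as well as grouping, and it sets the nine terms apart as additional, so an unwritten rule may govern them. In the copy of Appendix 2 read here, the hypersensitivity block carries no heading of its own, so a qualifier printed there would not be visible. This limits certainty about what would be programmed. It does not supply a rule, and if one exists, writing it down is most of the remedy.

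A sensitive list also has a purpose. Because investigators choose the best-fitting AE term, a true reaction may be recorded only as chills, fever or flushing. That is a reason to keep the terms, and to make them conditional rather than delete them.

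The mitigation is real but partial. PT rows and the IRR listing show which terms contribute, but PT rows cannot be added up to patients. The drug-related table is not an infusion filter: related includes doxorubicin, and a missing relationship counts as related. SAP 5.2.1.2 adds "Categories of AESI may be modified as the understanding of the safety of the investigational drug increases", but that note contains no timing rule.

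Four stronger readings are tempting, and the documents do not support them:
- *The SAP contradicts the protocol.* Grouping by PT is the protocol's own AESI rule in 10.3.1.3.
- *The overlap with Appendix 3 proves inflation.* One event in an AESI group and in a consolidated category is cross-classification, and says nothing about timing.
- *The data monitoring committee will see a wrong IRR rate.* SAP 5.17.2 specifies AESIs by PT and no group total.
- *A test loses power.* SAP 5.14.3 plans no between-arm AESI test; Fisher's test is specified in 5.14.2.1 for the overall AE summary.

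**Conclusion.** The point holds in a limited form. As written, the IRR AESI is a PT-only grouping that includes nine non-specific terms, with no infusion-timing condition and no use of the protocol's flag. Taken literally, the descriptive group total overstates the IRR rate in both arms and can dilute a difference between them.

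The size is unknown. The 4.5, 3.5 and 2.5 points tabulated in place of 5.0 rest wholly on assumed true and background rates, equal background in both arms, and independence. The gain from a window also depends on those assumptions. It is clear at 30% or 50% background, and absent for the difference at about 10% background if 10% of true reactions start late. This concerns a safety summary. The primary analysis and all controlled tests are untouched.

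**What to change.** In SAP 5.14.2 and Appendix 2, before the sponsor is unblinded:

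- Count the nine additional PTs in the IRR group total only when a non-imputed onset date falls on the day of an olaratumab/placebo infusion or the next calendar day. Whole days are used because the SAP handles AE onset as dates.
- Show events with an imputed onset date as timing unknown. Under SAP 5.4, a missing day in the month of first treatment becomes the day of first treatment, which is an infusion day, so an imputed date could satisfy the window artificially.
- Report the specific hypersensitivity terms and the nine conditional terms on separate rows.
- Keep the current all-PT grouping as a sensitivity table and present both.
- Use the hypersensitivity/IRR flag as a supporting definition if it was collected throughout. Check this first, because amendment (d) changed how IRRs are reported.
- Use the same definition in any premedication or antibody exploration of IRRs.

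The cost is a few lines of SAP text and some programming, since AE onset dates and study drug administration dates are already collected. The drawback is that true reactions starting after the window and coded only to the nine terms would count as IRRs only in the sensitivity table. In the illustration, 10% late reactions cost 5.0 × 0.1 = 0.5 points of the true difference, which is why both tables are needed.

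### The SAP's infusion-related reaction term list omits bronchospasm, a feature the protocol names in Grade 3-4 reactions, and the flag that could recover such events is not used

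*SAP*

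**What the plan says.** Three pieces of text have to be read together.

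- **What a severe reaction looks like.** Protocol 9.4.1.1.1.1 states: "A Grade 3 or 4 IRR will require immediate treatment, including the use of epinephrine, bronchodilators, and/or glucocorticoids for symptomatic bronchospasm". The same sentence goes on to the treatment of hypotension. These are the two manifestations it names.
- **How sites report it.** For signs or symptoms during or after an infusion, the same section says "investigators are encouraged to use the AE terms that best describe the event", and it asks sites to answer yes or no on a "hypersensitivity/IRR event flag". The umbrella term is not required.
- **How the SAP counts it.** SAP 5.14.2 says of the AESIs: "Each event is defined by a careful assessment and grouping of individual related MedDRA PTs", and refers to Appendix 2 for the terms. Appendix 2 has a block of hypersensitivity, oedema, shock and urticaria terms, followed by a row headed "Infusion-related Reactions (9 additional PTs". The SAP does not mention the flag.

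Protocol 10.3.1.3 lists infusion-related reactions as the only entry under "AESI for olaratumab/placebo". SAP 5.2.1.2 and 5.14.2 likewise give it as the only AESI for olaratumab alone.

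**The concern.** The protocol names two features of a severe reaction, and the SAP's list contains only one of them. A site that codes a reaction as bronchospasm because that describes it best is following the protocol, yet the event falls outside the group meant to capture it.

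The category matters. Protocol 9.1.1 records that Grade 3-5 reactions have been seen with olaratumab. Protocol 8.1.5 puts these reactions under iDMC review. Under 9.4.1.1.1.1 a Grade 3 or 4 reaction ends olaratumab/placebo for good. The term list feeds the AESI tables in SAP 5.14.3 and the interim safety tables in 5.17.2. It presumably also feeds the exploratory look at premedication against reaction rate and severity in 5.9.

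Specificity does not explain the gap, because the list already accepts back pain, pyrexia and three abdominal pain terms.

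**Working it through.** No sample-size formula applies. The check is a count and search of Appendix 2, followed by tracing how differently coded events would be tabulated.

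**Step 1: reproduce the plan's own figure.** The row announces 9 additional terms. They are abdominal pain, abdominal pain upper, abdominal pain lower, back pain, chills, dyspnoea, flushing, hypotension and pyrexia, which is 9. The stated figure is reproduced.

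**Step 2: count the whole group.** The block from Allergic oedema to Urticaria papular has 48 terms, so the group has 48 + 9 = 57. In the extracted text this block carries no label of its own and follows the arrhythmia terms. I read it as the base infusion-reaction list because it contains Infusion related reaction and because the next row calls its terms additional. The conclusion does not depend on this reading, since bronchospasm appears nowhere in Appendix 2.

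**Step 3: search.** Searching the 57 terms for the stems bronch and wheez gives 0 matches. Hypotension is present.

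**Step 4: could the term have been lost in extraction?** Unlikely. The 48-term block is in strict alphabetical order and runs from Angioedema to Circulatory collapse without a break where Bronchospasm would fall. In the other row, the stated count of 9 matches.

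**Step 5: trace the coding.**

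| How the reaction is reported | Infusion-reaction AESI | General tables |
|---|---|---|
| Bronchospasm only | Not counted | Shown under its own term |
| Bronchospasm at Grade 3 plus, say, flushing at Grade 1 | Counted, but at Grade 1 | Bronchospasm shown at Grade 3 |
| Bronchospasm plus a listed term of equal or higher grade | Counted in full | Both shown |
| Infusion related reaction, anaphylactic reaction or similar | Counted in full | Shown |

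Only the first two rows produce an error. The second matters only where the AESI is presented by grade or severity; SAP 5.14.3 describes its AESI summaries by group and preferred term.

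**Step 6: size.** If N patients have a true reaction and k of them are coded only as bronchospasm, the fraction missed is k/N. The documents give neither N nor k, so the fraction cannot be computed. With k = 0 it is zero.

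**After the fix:** 9 + 1 = 10 additional terms, and 57 + 1 = 58 in the group.

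**The case against.** The other side has several good points.

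- **The protocol's reporting examples point to listed concepts.** It defines reactions by the CTCAE version 4.0 entry and mentions allergic reaction, anaphylaxis and cytokine release syndrome as alternatives. Corresponding terms are in Appendix 2. Bronchospasm appears in a sentence about treatment, not in a reporting rule. This stands: coding a reaction as bronchospasm alone is permitted, not directed.
- **Airway involvement is largely covered.** A reader might infer that the list has no airway-narrowing terms. It does: laryngeal, laryngotracheal, tracheal, epiglottic and pharyngeal oedema are listed, as is dyspnoea. What is missing is the bronchoconstriction term that the protocol names.
- **The events are not hidden.** SAP 5.17.2 gives the iDMC treatment-emergent events by term, Grade 3-5 events, serious events by term with a listing, and events leading to discontinuation. SAP 5.14.3 has the matching final tables. This stands, and it limits the effect to the AESI grouping.
- **The flag exists, and the SAP leaves room to revise.** The data needed to recover such events are collected, and SAP 5.2.1.2 allows AESI categories to be modified. Both make the repair easy, but no current text uses the flag or adds the term.

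None of this removes the mismatch between the protocol's named features and the SAP's list.

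**Conclusion.** The point holds as a minor gap in a term list. Applied as written, Appendix 2 leaves a reaction coded only as bronchospasm out of the AESI summaries, and may place one reported with a milder listed term at too low a grade.

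Three stronger readings are tempting, and the documents support none of them.

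- **That the severe-reaction rate is understated overall.** The same list counts back pain, abdominal pain, pyrexia and dyspnoea, and neither SAP 5.14.2 nor Appendix 2 ties them to infusion timing. Unrelated events could push the count the other way, so the net direction is unknown.
- **That the loss falls almost wholly on the olaratumab arm.** No arm-level reaction rates are given, both arms receive doxorubicin, and protocol 9.2.2 itself provides for a reaction to doxorubicin.
- **That a sizeable share is lost.** One could assume a 3% Grade 3-4 rate among 230 olaratumab patients (0.03 x 230 = 6.9, about 7), with 1 or 2 coded only as bronchospasm, giving 1/7 = 14% or 2/7 = 29%. Both inputs are invented. The denominator is also Grade 3-4 reactions only, whereas the AESI tables are not described as restricted by grade. The loss may be zero.

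The conclusion rests on two assumptions: that Appendix 2 as extracted is complete, and that AESI membership follows the list alone, as SAP 5.14.2 implies.

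**What to change.** Before database lock, add Bronchospasm to the infusion-related reaction group in SAP Appendix 2 and change the row heading from 9 to 10 additional terms. Preferably count it when the hypersensitivity/IRR flag is yes, so that unrelated bronchospasm is not drawn in, and state that rule in SAP 5.14.2. Apply the updated list to the iDMC tables and to the final AESI summaries and listing.

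Wheezing and stridor could be added under the same rule, but the documents do not name them, so they are optional.

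The cost is a short SAP edit and a rerun of the affected tables. No new data are needed, and efficacy analyses, alpha and treatment rules are untouched. With the flag condition, the count depends on sites completing the flag; unflagged bronchospasm would still show in the general tables. Without it, a few events unrelated to the infusion may enter the group.
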